Potential subjects will contact the principal investigator, [name] for preliminary screening and if they are able to satisfy the basic criteria, will be invited for formal screening. If qualified, they will be enrolled to begin the study. In order to avoid any undue pressure, all potential subjects who are patients of one of the Investigators will be given the option to do any or all of the following:

- Offer patients the opportunity to take home the Consent Form, and call back if they wish to participate
- Offer to connect the patient with other health care providers to discuss participation.

All study subjects will be screened and evaluated at the Foot and Ankle Clinic at MGH Waltham. Screenings and enrollments will take place on Tuesdays and Wednesdays, during dedicated research time.

The conditions being examined here are common among all races and genders, and enrollment is open to all. There have been limitations placed on subject age, as this age group is most likely to experience the conditions being studied.

5. Subject Enrollment

Prescreening is done by telephone, and is performed by the Principal Investigator or one of the research assistant. The following script is used to make a preliminary determination of eligibility. Before asking any other questions, the following questions and points will be discussed with the potential study subject:

- *Is this a good time to talk?*
- *Would you be willing to answer questions about your health and medical history to find out if you might qualify for the study? Some of the questions may make you feel uncomfortable. You can stop at any time.*
- *I will record your answers in writing, but only collect detailed contact information if you qualify for the study and want to schedule an in person visit.*
- *The risk of allowing us to collect and record your name with your answers is a loss of confidentiality. We will take reasonable steps to protect the confidentiality of your information.*
- ***May I begin?***

This is a study to evaluate the effect of arch supports on people with one or more of the following conditions: Bunions (also known as hallux valgus), Heel pain (also known as plantar fasciitis), metatarsalgia (pain across the ball of your foot), and/or lower back pain that gets worse with walking around. Do you have any (or all) of these conditions, and have these symptoms been present for at least 30 days?

• No

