o Thank you for your interest. You do not qualify to participate in this study but if you like, you may leave your name with us to participate in future studies.

• Yes

Before I describe the rest of the study to you, I have a few more questions to determine if you qualify.

Are you between the ages of 18 and 65 years old? Do you weigh less than 300 lbs.?

• No

o Thank you for your interest. You do not qualify to participate in this study but if you like, you may leave your name with us to participate in future studies.

• Yes

Mass General Brigham Institutional Review Board
Intervention/Interaction Detailed Protocol

Have you had surgery to your feet previously (not including toenail procedures)? Have you ever had any part of either foot amputated?

· Yes

o Thank you for your interest. You do not qualify to participate in this study but if you like, you may leave your name with us to participate in future studies.

· No

Is the difference in shoe size between your two feet 2 or more full sizes?

· Yes

o Thank you for your interest. You do not qualify to participate in this study but if you like, you may leave your name with us to participate in future studies.

· No

Do you currently wear custom-molded orthotics, or have you worn them in the last 30 days?

· Yes

o Thank you for your interest. You do not qualify to participate in this study but if you like, you may leave your name with us to participate in future studies.

· No

Have you ever been diagnosed with Neuropathy?

· Yes

o Thank you for your interest. You do not qualify to participate in this study but if you like, you may leave your name with us to participate in future studies.

· No

Allow me to tell you a little more about this study. We will be looking at the effect of arch supports on a variety of conditions, including bunions, metatarsalgia, plantar fasciitis, knee, hip, and/or lower back pain. We want to determine if wearing arch supports might help to relieve pain associated with these conditions.

In order to participate, you will be asked to go to come into the Good Feet store to be fitted for the arch support kit and for a new pair of shoes. You will then be referred to the Foot and Ankle clinic at Massachusetts General Hospital in Waltham, where you will receive the shoes and arch supports and be enrolled into the study.

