There will be a total of 4 visits that are required. The first visit is the longest and will take approximately 2 hours. The 2nd, 3rd, and 4th visits are only expected to take about 45 minutes.

At the first visit, the doctor there will also examine your feet and discuss your medical history with you. You will then be asked to sign a consent form to participate in the study.

After signing the consent form, you will receive your new arch supports and your new shoes. They will then do a series of tests that include:

- o Standing Catscan (CT scan) of both feet, with and without arch supports*
- o Standing X-rays of both feet, with and without arch supports*
- o You will be asked to complete a questionnaire*

During the 2nd, 3rd, and 4th visits, you will be asked to complete the questionnaire again, and the doctor will examine your feet.

If you decide to participate in the study, you will receive the arch supports and shoes at no cost to you. You may keep these after the study as well. In addition, we can reimburse you for any travel costs. You will receive a check for \$200 at the end of the study. If this sounds like something that you would be willing to do, I will need to get a little more contact information from you so that I can schedule your visits.

After preliminary screening, potential study subjects will be scheduled for an in-person meeting and evaluation, in order to review the study expectations. Subjects who are not registered in the MGB system will be asked to register prior to their first appointment. All subjects will be informed that their ability to receive treatment in our clinic will not be influenced by whether or not they participate in this study. Once we have reviewed the study plan, eligible subjects will be asked to sign an informed consent that will be given on an paper or and iPad via RedCap and signed, to be administered by the Principal or Co-investigator, and signed in the presence of a witness. Study subjects do not have to sign the consent on the spot, and may take the form with them, if they decide they would like to review at home, before signing.

Any subjects drawn from the principal and co-investigator's practice will be given clear indications that they are under no obligation whatsoever to participate in this study, and that either way, it will not hinder their ability to continue to be treated by the investigator.

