Non-english speaking study subjects, can review information with the help of a medical translator. Translated documents will be provided as needed. The Short Form consent process will be used to obtain consent from non-English speaking study subjects.

Informed Consent

Informed consent will be obtained from each subject before any procedures or assessments that would not otherwise be required for the care of the subject are done and after the aims, methods, anticipated benefits, potential hazards, and insurance arrangements in force are explained and the subject has been given sufficient time to ask questions and consider participation in the study. It will also be explained to the subjects that they are free to refuse entry into the study and free to withdraw

from the study at any time without prejudice to future treatment. It is permissible for a third person (e.g., a family member) to be present during the explanation of the study.

The written informed consent form is to be in compliance with Code of Federal Regulations (CRF) 21 Part 50.27 and Good Clinical Practice (GCP) guidelines. The Sponsor will approve the informed consent and all amendments to the informed consent prior to submission to the IRB/Ethic's Committee. A copy of the informed consent document to be used will be submitted by the Investigator to the IRB/Ethic's Committee for review and approval prior to the start of the study. The original signed consent is retained in the subject's study records, and a copy is provided to the subject and placed in medical record.

Study participants are not being offered anything of significant value that may be viewed as coercive in nature, and is appropriate for the time and effort commitment requested from all study subjects.

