6. STUDY PROCEDURES

Table 1: Schedule of Visit Activities

Study Procedures	Screening and Treatment	Follow-up Visits (Every 28±3 days)			
		Week 0	Week 4	Week 8	Week 12
		Visit 1	Visit 2	Visit 3	Visit 4
Informed Consent	X				
Inclusion/Exclusion Criteria	X				
Medical History and Demography	X				
Urine Pregnancy test for women	X				
Physical Exam (incl Ht & Wt)	X	X	X	X	
Selection and fitting of insoles	X				
Clinical assessment of Foot Function	X	X	X	X	
Weightbearing CT w & w/o insoles	X				
Weightbearing X-ray w & w/o insoles	X				
Administer VAS, OFS exam	X	X	X	X	
Review Diary		X	X	X	
Schedule subsequent visits	X	X	X		
Record Adverse Events		X	X	X	

a. Screening / Baseline – Visit 1 (Day 1)

Informed consent must be obtained from each subject before any study procedure can commence. The consent form will be given on an IPad via RedCap signed on paper. The subject will sign and date the Informed Consent Form and undergo the following evaluations/procedures:

Medical History and Physical Assessment

- Determination of eligibility based on inclusion/ exclusion criteria
 - Urine pregnancy test for all women. Pregnant women are not eligible to participate.
- Demographics (date of birth, gender, race) will be recorded
- Medical history: relevant medical history, including history of current disease, and information regarding underlying diseases will be recorded.
- Physical exam will be performed and results recorded
- Height and weight will be measured and recorded.
 - Calculate subject's Body Mass Index

Foot Assessment

- Clinical evaluation of feet will be performed by Podiatrist Study Investigator
 - Classification of foot type
 - Pathologies and painful conditions will be identified
 - Additional ancillary conditions will be included in the history
 - Back, Knee, and Ankle pain along with associated diagnoses and prior treatments
 - Dermatologic conditions
 - Neurovascular measurements
 - Assessment of standard shoe gear
 - Generalized foot appearance (i.e. edema, tender areas, etc.)
 - Basic gait assessment

Subjective Pre-Treatment Assessment:

- VAS (Visual Analog Scale) and OFS (Orthopedic Foot Score) data collected to determine pre-treatment levels of pain and function. The following validated questionnaires will be completed by each study subject.
 - ACFAS Universal foot Evaluation
 - AOFAS Outcome score
 - Oswestry Low Back Disability score
 - Pain Intensity Score
 - Global Health Test
 - Pain Interference

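### The phone script puts a store fitting before consent and the device before the baseline questionnaire; Section 6a implies the reverse order but does not fix it

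*Combined protocol and SAP*

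**What the plan says.** **Prescreening script (Section 5).** Candidates are told: "In order to participate, you will be asked to go to come into the Good Feet store to be fitted" for supports and shoes. They are then referred to the clinic, "where you will receive the shoes and arch supports and be enrolled into the study". At that first visit the doctor examines the feet and goes through the history, and after that the candidate is asked to sign consent. The script continues: "After signing the consent form, you will receive your new arch supports and your new shoes. They will then do a series of tests". The tests listed are standing CT and standing X-ray, each with and without supports, and a questionnaire. At Visits 2 to 4, "you will be asked to complete the questionnaire again".

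**Consent rules.** The Informed Consent text in Section 5 requires consent "before any procedures or assessments that would not otherwise be required for the care of the subject are done". Section 6a is stricter: no study procedure may start before consent, with no exception.

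**Table 1 (Section 6).** "Selection and fitting of insoles" and "Administer VAS, OFS exam" are both listed as study procedures and marked at Visit 1. No store visit appears.

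**Section 6a.** After consent come history, physical examination and foot assessment, then a block headed as the subjective pre-treatment assessment, then insole selection based on the clinical assessment, then imaging. The pre-treatment block is to be completed on day one. It also asks for the subject's immediate impressions without and with the support.

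**Other text outside the script.** In Section 4 the store displays a poster and refers people to the clinics, and "All study subjects will be screened and evaluated at the Foot and Ankle Clinic at MGH Waltham". The paragraph after the script in Section 5 describes an in-person meeting and evaluation followed by consent. Neither mentions a store fitting.

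**The concern.** Two sequences are in conflict, and they have different consequences.

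The first is consent. The script makes the store fitting a condition of participation and puts it before the visit at which consent is signed. If that fitting is the study procedure in Table 1, a site that follows the script performs a study procedure on people who have not consented. The script also puts the foot examination and history before the signature, where Section 6a puts them after it.

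The second is the baseline. The primary endpoint is self-reported change in symptoms from baseline, in one arm with no control, and Section 9 defines its effect sizes as differences from baseline. Staff who follow the script would collect the questionnaire after the supports and shoes are handed over; staff who follow the list in Section 6a would collect it before. These are different baselines, and no comparison group would absorb the difference.

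**Working it through.** The documents give no figure to reproduce here. The check is a comparison of sequences, followed by one line of algebra.

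**Step 1. Order of events by source.**

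| Source | Order |
|---|---|
| Script, Section 5 | store fitting → foot exam and history → consent → supports and shoes received → CT, X-ray, questionnaire |
| Section 6a, list order | consent → history and exams → questionnaires and VAS → impressions without and with support → insole selection and fit check → imaging |
| Table 1 | all at Visit 1; no order within the visit stated |

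**Step 2. Fitting against consent.** Table 1 calls fitting a study procedure, and Section 6a puts every study procedure after consent. The script's fitting precedes the consent visit. The ordinary-care exception in Section 5 does not plausibly cover a step done in order to take part, and Section 6a has no such exception. A fitting held before the clinic visit also cannot follow the clinical assessment on which Section 6a bases the selection of insoles. The script hands over the devices only after consent, so the conflict concerns the fitting and not the dispensing.

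**Step 3. Exam and history against consent.** Section 6a lists both among the evaluations that follow the signature; the script has them before it. For a subject who is already a clinic patient, the Section 5 exception might cover them as ordinary care. Section 6a as worded does not.

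**Step 4. Questionnaire against device.** The script's Visit 1 questionnaire is the baseline one, because it is completed again at Visits 2 to 4. It belongs to the tests that follow receipt of the supports. Section 6a's heading, purpose and list position all point the other way. No sentence there places the scores before first contact with the device, and the same block contains an item that needs the support in place.

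**Step 5. What a shifted baseline does.** Let B be the mean score before any device contact, s the mean shift that contact causes in the recorded baseline, and Y4, Y8 and Y12 the follow-up means.

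- Recorded baseline = B + s
- Recorded change at week k = Yk − (B + s) = (Yk − B) − s, for k = 4, 8, 12

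All 3 changes move by −s. The numerator of each Cohen's d for difference from baseline moves by the same amount. The equality is exact when the same subjects contribute at each visit. Comparing Weeks 4, 8 and 12 with one another cannot reveal s, because it cancels. The documents supply neither a value nor a sign for s.

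**The case against.** The strongest reply is that Section 6a is the governing procedure and the script is a lay telephone summary for preliminary eligibility. On that view the intended order is clear, the script is the outlier, and only its wording needs repair. Much of this stands: Section 6a does show the intent, and the script is where most of the correction belongs. But the script is protocol text that tells candidates where to go and in what order, and what it says on both points is contrary to the body. A label and a list position are weak protection when another part of the same document states the reverse.

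Some stronger readings are tempting and should not be adopted:

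- A reader might infer from the row order of Table 1 that the scores come after fitting and imaging. The table sets no order within a visit, so it is evidence for neither side.
- A reader might take Section 6a's instruction to confirm fit before other data collection as covering the questionnaires. It closes the insole block and leads straight into imaging, which is its natural meaning.
- A reader might assume that supports are worn at the store. The documents do not say so; the step could be sizing only. The baseline question at Visit 1 arises without it.
- A reader might conclude that the treatment effect is biased upward. Contact could move the recorded score either way, and nothing in the documents says which, or whether it moves at all.

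**Conclusion.** The conflict in the text is certain on both points. The script puts a required store fitting, and also the exam and history, before the consent signature, and it puts the baseline questionnaire after receipt of the device. The protocol body points to the opposite order. It fixes that order by rule for consent, and only by label and list position for the scores.

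The breach of the consent rule is conditional on the store step being the fitting that Table 1 lists. The effect on the primary endpoint is conditional on scores being taken after device contact and on contact altering them. If both hold, all 3 follow-up changes move by one common amount whose size and direction cannot be derived from the documents. It would go too far to say that the protocol as a whole places baseline scores after the device. The matter should be fixed, because it touches consent and the only baseline of a single-arm study and the correction is cheap.

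**What to change.** Correct the prescreening script so that it matches Section 6a, including the place of the foot exam and history relative to consent.

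Add one sentence to Section 6a, and a matching note to Table 1, along these lines: consent is signed first; all baseline questionnaires and the VAS are completed next; no fitting or try-on of supports or shoes, at the store or the clinic, takes place before both are done. State that the immediate impressions are recorded afterwards and are not part of the baseline value.

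The cost is one IRB amendment. If the store is still used, its fitting has to be rescheduled to follow consent and baseline scoring, which may mean an extra trip for subjects.

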6. STUDY PROCEDURES

Table 1: Schedule of Visit Activities

Study Procedures	Screening and Treatment	Follow-up Visits (Every 28±3 days)			
		Week 0	Week 4	Week 8	Week 12
		Visit 1	Visit 2	Visit 3	Visit 4
Informed Consent	X				
Inclusion/Exclusion Criteria	X				
Medical History and Demography	X				
Urine Pregnancy test for women	X				
Physical Exam (incl Ht & Wt)	X	X	X	X	
Selection and fitting of insoles	X				
Clinical assessment of Foot Function	X	X	X	X	
Weightbearing CT w & w/o insoles	X				
Weightbearing X-ray w & w/o insoles	X				
Administer VAS, OFS exam	X	X	X	X	
Review Diary		X	X	X	
Schedule subsequent visits	X	X	X		
Record Adverse Events		X	X	X	

a. Screening / Baseline – Visit 1 (Day 1)

Informed consent must be obtained from each subject before any study procedure can commence. The consent form will be given on an IPad via RedCap signed on paper. The subject will sign and date the Informed Consent Form and undergo the following evaluations/procedures:

Medical History and Physical Assessment

- Determination of eligibility based on inclusion/ exclusion criteria
 - Urine pregnancy test for all women. Pregnant women are not eligible to participate.
- Demographics (date of birth, gender, race) will be recorded
- Medical history: relevant medical history, including history of current disease, and information regarding underlying diseases will be recorded.
- Physical exam will be performed and results recorded
- Height and weight will be measured and recorded.
 - Calculate subject's Body Mass Index

Foot Assessment

- Clinical evaluation of feet will be performed by Podiatrist Study Investigator
 - Classification of foot type
 - Pathologies and painful conditions will be identified
 - Additional ancillary conditions will be included in the history
 - Back, Knee, and Ankle pain along with associated diagnoses and prior treatments
 - Dermatologic conditions
 - Neurovascular measurements
 - Assessment of standard shoe gear
 - Generalized foot appearance (i.e. edema, tender areas, etc.)
 - Basic gait assessment

Subjective Pre-Treatment Assessment:

- VAS (Visual Analog Scale) and OFS (Orthopedic Foot Score) data collected to determine pre-treatment levels of pain and function. The following validated questionnaires will be completed by each study subject.
 - ACFAS Universal foot Evaluation
 - AOFAS Outcome score
 - Oswestry Low Back Disability score
 - Pain Intensity Score
 - Global Health Test
 - Pain Interference
- Pre-treatment assessment to be completed on day one.
- Subjects will describe their immediate impressions without and with the arch support in place.

Insole Selection

- Based on clinical assessment, properly sized set of arch supports and properly fitted athletic shoes will be dispensed to the study subject. Fit and comfort will be confirmed before proceeding with other data collection steps.

Baseline Measurements

- Each subject will have one weight bearing CT and one weight bearing X-ray series (AP/Lateral) taken barefooted and a second series taken with the selected arch support in place. Subjects are enrolled sequentially, and there is no placebo group.
- Image analysis will compare position and alignment of bones of the foot to measure differences in positioning with and without arch supports, using CT and X-ray. X-ray measurements will include intermetatarsal angles, hallux abductus angle, sesamoid position, metatarsal declination angle, calcaneal inclination angle, talocalcaneal angle, calcaneocuboid angle, and overall morphology. CT measurements will be used to determine the 3-dimensional positioning of the foot bones, and will document the change in position that occurs with and without arch support.

Logging of Activities and Symptoms

- Study subjects will be issued a diary and they are to record the following data on a weekly basis. The diary will be sent to the patient via email and RedCap links.
 - Estimated distance walked (Those able to count steps are encouraged to do so.).
 - Activities of Daily Living
 - Symptoms, and level of pain rated on a VAS scale.
 - Compliance with wearing of insoles and athletic shoes

b. Treatment Phase

We will be conducting follow up surveys via email and RedCap links with patients.

Monthly follow up (End of weeks 4, 8, and 12)

- Confirmation of eligibility based on inclusion/ exclusion criteria
- Medical history: New or relevant changes to medical history, including history of current disease, and information regarding underlying diseases will be recorded
- Review of logged data from daily diary
- Completion of physician re-assessment and OAS and VAS scoring.
- Validated questionnaires will be completed at each of the 3 follow-up visits.
 - ACFAS Universal foot Evaluation
 - AOFAS Outcome score
 - Oswestry Low Back Disability score
 - Pain Intensity Score
 - Global Health Test
 - Pain Interference
- Record any Adverse Events
- Clinical photographs will be taken with and without the arch support in place, while barefooted.

c. Study Completion/Termination

When the subject completes the study, voluntarily withdraws, is withdrawn for any reason, the study is terminated, or the Investigator is no longer able to locate the subject, the reason for the withdrawal will be reported along with any relevant information concerning the device, subject condition or death.

All subjects withdrawn from the study due to an adverse event, or have an adverse device effect or serious adverse event at study completion, will be followed until the adverse device effect or serious adverse event is resolved, a resolution is no longer expected or it returns to baseline.

Treatment Discontinuation

After completing the estimated 12-week visit requirements, the subject will be considered to have completed the study. In all cases of withdrawal, the date and the reason for withdrawal are to be documented.

Primary Endpoint

The primary endpoint is the change in symptoms when arch supports are worn, as compared to baseline. Change in symptoms and relief of pain will be quantified based on subjective completion of validated questionnaires. Data from the questionnaires will provide a reliable assessment of symptomatic relief from the foot ailments being evaluated.

Secondary Endpoint

The secondary endpoint is the change in foot morphology when shoe inserts are worn. The change to be documented is the acute change that occurs in the boney structure of the foot when it is supported with the orthosis. A critical part of the analysis is to demonstrate if there are measurable changes in foot morphology when supported, and to determine if those changes correlate with symptomatic changes in the study subject's foot condition.

Remuneration

Study subjects will not be paid to participate in this study. However, all participants will receive new orthoses and new shoes, and will be permitted to keep these items at the conclusion of the study. Also, all study participants will receive up to \$50 to reimburse them for any travel expenses related to the study. We would like to pay the participants by check on the date of their visit, if permitted to do so.

Sharing of Data and Confidentiality

All data will be kept within the confines of MGH. Since there are no other sites involved in the study, no outside investigators will have a need for access to the data.

7. Risks and Discomforts

The risks include discomfort during walking and/or standing, and can include bruise and/or blister formation, exacerbation of existing foot pain, tightness in shoes, temporary foot or leg cramps, bruising of the foot. X-rays and CT scans will be taken, and these tests involve very low levels of radiation. All of the devices being used in this study are currently available for purchase without a prescription, and are being used in the manner in which they were intended.

There are no new applications being explored for either the insoles or shoes that the study subjects will receive during this study. There are no unusual or excessive risks to study subjects, and all procedures being performed on subjects are already in use for diagnostic and treatment purposes.

8. Benefits

Historically, when these conditions (plantar fasciitis, hallux valgus, metatarsalgia) are treated with arch supports, they have responded with significantly less pain, and in many cases, helped the subjects to avoid surgical correction. We expect that the subjects who participate in this study will show signs of improvement in symptoms. They will also benefit from a highly focused medical examination of their

feet. Future patients will benefit from this study by knowing that arch supports are a safe and effective treatment for these foot ailments. The study may also help to optimize arch support design in the future.

9. Statistical Analysis

Statistical plan is for a one-way repeated measures ANOVA to compare the parameters with participants with and without arch-support insoles for each slope. We anticipate using SPSS for Windows (SPSS Science Inc., Chicago, IL, USA) for the statistical analyses. Levene's test will be used to test the homogeneity of the variances. A Kolmogorov-Smirnov test will be used to evaluate the normality of the data, a Wilcoxon test will be used when the data are not normally distributed. The significance level was set at $\alpha = 0.05$. The effect size (ES) for the difference from baseline will be calculated for each variable as a measure of the practical relevance of the significance using Cohen's d ; ES values between 0.20 and 0.49 are considered small, those between 0.50 and 0.79 are considered moderate, and those 0.80 and above are considered large.

10. Monitoring and Quality Assurance

In order to insure subject safety, all data will be reviewed at each study visit, including a thorough review of the study subject diary. This will occur on a monthly basis. In addition, study subjects will have the unlimited opportunity to contact the Principal Investigator to discuss any concerns or complications, at any time. The Principal investigator will be responsible for assessing any risks or complications, and will discontinue the study if any related complications occur.

In this study, the DSMB will be composed of other physicians from the PI's department who are not participating in the study. Members of the DSMB will meet bi-weekly to discuss and review all research data pertaining to safety in the current study, until the completion of the study. This group will also be responsible for maintaining the integrity of all recordkeeping. All adverse events will be reported to the DSMB, Partners' IRB and Study Sponsor.

Study Monitoring will be performed in accordance with ICH E6-GCP, sponsor's SOPs, the protocol, and applicable local regulations. According to ICH E6-GCP, the sponsor or the authorized personnel on behalf of the sponsor may audit the investigational site to compare raw data, source data, and associated records with the interim or final report of the study to assure that data have been accurately reported. The investigators will accept that regulatory authorities may conduct an inspection to verify compliance of the study with GCP.

11. Privacy and Confidentiality

- ✓ Study procedures will be conducted in a private setting
- ✓ Only data and/or specimens necessary for the conduct of the study will be collected
- ✓ Data collected (paper and/or electronic) will be maintained in a secure location with appropriate protections such as password protection, encryption, physical security measures (locked files/areas)

- N/A** Specimens collected will be maintained in a secure location with appropriate protections (e.g. locked storage spaces, laboratory areas)
- Data and specimens will only be shared with individuals who are members of the IRB-approved research team or approved for sharing as described in this IRB protocol
- Data and/or specimens requiring transportation from one location or electronic space to another will be transported only in a secure manner (e.g. encrypted files, password protection, using chain-of-custody procedures, etc.)
- All electronic communication with participants will comply with Mass General Brigham secure communication policies
- Identifiers will be coded or removed as soon as feasible and access to files linking identifiers with coded data or specimens will be limited to the minimal necessary members of the research team required to conduct the research
- All staff are trained on and will follow the Mass General Brigham policies and procedures for maintaining appropriate confidentiality of research data and specimens
- The PI will ensure that all staff implement and follow any Research Information Service Office (RISO) requirements for this research
- Additional privacy and/or confidentiality protections

The investigators will assure that the privacy of the subjects, including their personal identity and all other personal medical information, will be maintained at all times. In CRFs and other documents or material submitted to the sponsor, subjects will not be identified by their names, but by an identification code (e.g., initials and study allocated number). Personal medical information may be scrutinized for the purpose of verifying data recorded in the CRF. The monitors, properly authorized persons on behalf of the sponsor, the quality assurance unit, or regulatory authorities may do this. Personal medical information will always be treated as confidential.

The Investigator will maintain the confidential subject identification list, that will not to be made available to the Sponsor, including subject's, study Identification and medical record numbers to link records. The subject should be informed that the data will be stored and analyzed by computer, that local and Federal regulations for the handling of computerized data will be followed and that identification of individual subject data will only be possible for the Investigator and the monitor. The subjects will be identified in the Case Report Form with subject number and initials. The Investigator should inform the subject that the records relevant to the study may be inspected by the study Sponsor, the FDA, or other persons as required by law.

12. References

1. Nawoczenski DA, Ludewig PM: The effect of forefoot and arch posting orthotic designs on first metatarsophalangeal joint kinematics during gait. *J Orthop Sports Phys Ther* **34**: 317, 2004.
